7.2. Exclusion Criteria

Patients who meet any of the following criteria cannot participate in this study:

- 1) Patients who have received any of the following treatments:
 - a) Treatment with dupilumab or any anti-IL-4R α or IL-13 antibody treatment;
 - b) Topical drugs for treatment of AD or have the potential to affect the assessment of AD, including but not limited to corticosteroids, PDE-4 inhibitors, Janus kinase (JAK) inhibitors, aromatic hydrocarbon receptor agonists, tacrolimus or pimecrolimus, or traditional Chinese medicine (TCM) or herbal medicine, etc. within 2 weeks before baseline;
 - c) Have undergone bleaching baths \geq twice within 2 weeks before baseline;
 - d) Have begun to use prescription emollients or emollients containing additives (e.g., ceramide, hyaluronic acid, urea, or filaggrin breakdown products) to treat AD from

the screening period (if the subject has started using this kind of emollient before the screening visit, they can continue to use it at a stable dose; if the subject is intolerable to the emollients provided uniformly by the sponsor during the screening period, he/she can change to emollient of this kind used previously, but it must be used at a stable dose for at least 7 days before baseline and during the study period);

- e) Treatment with systemic corticosteroids or other immunosuppressive/immunomodulating substances (e.g., cyclosporine, mycophenolate mofetil, azathioprine, methotrexate, or oral JAK inhibitors) due to AD or other diseases within 4 weeks before baseline (*except for corticosteroid inhalers and nasal sprays*);
- f) Treatment with systemic TCM or herbal treatment within 4 weeks before baseline (note: except for those for the treatment of diseases other than AD, which are necessary and will neither increase the risks of the subjects nor affect the assessment of the study in accordance with the medical judgements of the investigator and/or specialist physician);
- g) Treatment with phototherapy (narrow band ultraviolet B [NBUVB], ultraviolet B [UVB], ultraviolet A1 [UVA1], psoralen + ultraviolet A [PUVA]), sunbed or any other light emitting device (LED) therapy within 4 weeks before baseline;
- h) Have used any investigational drug/treatment within 4 weeks before baseline or 5 drug half-lives, whichever is longer;
- i) Treatment with other biological agents (e.g., omalizumab) within 3 months before baseline or 5 drug half-lives (if known), whichever is longer;

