7.4.2. Intercurrent events and handling strategies

See table below for intercurrent events and handling strategies of the primary analysis:

Label	Intercurrent event	Strategy	Remarks
Intercurrent event 1 (use of prohibited drugs/treatments specified in the protocol for which the study treatment must be early terminated due to poor response)	
• Dupilumab or any anti-IL-4Rα or IL-13 antibodies;• Topical PDE-4 inhibitors or JAK inhibitors;• Systemic treatment with corticosteroids or other immunosuppressive and/or immunomodulatory agents, such as cyclosporine, mycophenolate mofetil, azathioprine, methotrexate, or oral JAK inhibitors;• Cell depletion agents (e.g., rituximab) or other biological agents;• Other investigational drugs (non CBP-201) or treatments. 
Due to the poor response, the above prohibited drugs/treatments have been used before the W16 visit.
	Composite strategy	
This type of intercurrent event occurs because of poor response, should be treated as non-response.
 
If it is a continuous variable, the data after the occurrence of the intercurrent event should be imputed with WOCF.

Intercurrent event 2 (use of other prohibited drugs/treatments specified in the protocol other than those in Intercurrent Event 1, with a	
• Initiation of SIT, or dose up-regulation;• TCS or TCI;• Phototherapy (NBUVB, UVB, UVA1, PUVA), sunbed or any other LED therapies;• Bleaching baths more than 2 times a week;• Any drug for the treatment of AD (except	Treatment policy strategy	
The impact on the assessment of efficacy endpoints can be ignored, and the actual observed value is used. If the actual observed value is missing, it will be processed

Label	Intercurrent event	Strategy	Remarks
negligible impact on the assessment of the primary endpoint)	
mild emollients) that may interfere with the evaluation of efficacy results or affect the evaluation of AD severity.
 
The cumulative duration of use of the above prohibited drugs/treatments before the W16 visit is no more than 7 days, and the end date is at least 4 weeks away from the W16 visit.
		according to the principle for processing missing values.

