Intercurrent event 3 (use of other prohibited drugs/treatments specified in the protocol other than those in Intercurrent Event 1 due to poor response, with a major impact on the assessment of the primary endpoint)	
 Initiation of SIT, or dose up-regulation; TCS or TCI; Phototherapy (NBUVB, UVB, UVA1, PUVA), sunbed or any other LED therapies; Bleaching baths more than 2 times a week; Any drug for the treatment of AD (except mild emollients) that may interfere with the evaluation of efficacy results or affect the evaluation of AD severity. 
The cumulative duration of use of the above prohibited drugs/treatments due to poor response before the W16 visit is more than 7 days, or the end date is less than 4 weeks away from the W16 visit.
	Composite strategy	
This type of intercurrent event occurs because of poor response, should be treated as non-response.
 
If it is a continuous variable, the data after the occurrence of the intercurrent event should be imputed with WOCF.

Intercurrent event 4 (premature discontinuation of treatment/EOT due to AEs)	The subject experiences an AE or SAE that is considered by the investigator to be intolerable before the W16 visit, and is unsuitable for continuing the study treatment, resulting in premature discontinuation of treatment/EOT.	Composite strategy	
This type of intercurrent event occurs because of poor safety of treatment, should be treated as non-response.
 
If it is a continuous variable, the data after the occurrence of the intercurrent event should be imputed with WOCF.

Intercurrent event 5 (the subject's administration is missing due to the COVID-19 epidemic)	The administration at two consecutive visits (W12 and W14) immediately before the W16 visit is missing or the administration in the Stage 1 treatment period is missing for ≥ 3 times.	Hypothetical strategy	The observed values are not used, and the J2R (jump to reference) method is used for imputation.
Intercurrent event 6 (use of prohibited	The following prohibited drugs/treatments have been used before the W16 visit not because of the poor response:	Hypothetical strategy	The observed values are not used, and the J2R (jump to

Label	Intercurrent event	Strategy	Remarks

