7.4.4. Other efficacy endpoint analysis

The categorical efficacy endpoint analysis in Stage 1 will be performed using the same method as the primary efficacy endpoint analysis.

The continuous efficacy endpoint analysis in Stage 1 will be performed using the same method as the secondary efficacy endpoint analysis.

According to the investigator's judgment, AD aggravation or deterioration of symptoms which requires drugs or treatments originally prohibited by the protocol for rescue therapy will be defined as "AD recurrence" event.

The number of AD recurrence, the number of subjects with AD recurrence, and the number of days of AD recurrence in Stage 1, from baseline to W8, from W9 to W16 will be analyzed. The total number of AD recurrence in each stage will be summarized. AD recurrence will be summarized by the number of recurrences, that is, 0, 1, 2 and ≥ 3 . The number and percentage of subjects will be calculated. Chi-squared test will be adopted to compare whether the differences between the two groups are statistically significant. The total number of subjects with AD recurrence in each stage will be summarized, and the number and percentage of subjects will be calculated. Chi-squared test will be performed to compare whether the differences between the two groups are statistically significant. The number of days of AD recurrence in each stage will be summarized by descriptive statistics.

7.4.5. Efficacy analysis in stage 2

During efficacy analysis in Stage 2, the percentage of subjects achieving efficacy endpoint and its confidence interval will be calculated for categorical efficacy endpoints. For continuous efficacy endpoints, ANCOVA model will be used to calculate the mean, the Least Square Mean, 95% confidence interval and SE of the change from baseline and percentage change from baseline of each efficacy endpoint. The model will include treatment group, severity of baseline disease (IGA 3 or 4), and baseline value of corresponding endpoint. Inferential statistics will not be performed during the Stage 2 analysis. The following two analyses will be performed.

Analysis method 1: Categorical efficacy endpoints after the occurrence of events will be regarded as no response for subjects who have the following conditions; continuous efficacy endpoints after the occurrence of events will be imputed using WOCF in Stage 2; other missing data except for the conditions above will be imputed using multiple imputation (MI).

- Group adjustment

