- Premature discontinuation of treatment/EOT due to AEs
- Use of prohibited drugs/treatments specified in the protocol as a rescue treatment for AD due to poor response, which has a major impact on the assessment of the efficacy endpoints, including:

The following prohibited drugs/treatments are used during Stage 2 (W16 to W52):

- Dupilumab or any anti-IL-4R α or IL-13 antibodies;
- Topical PDE-4 inhibitors or JAK inhibitors;
- Systemic treatment with corticosteroids or other immunosuppressive and/or immunomodulatory agents, such as cyclosporine, mycophenolate mofetil, azathioprine, methotrexate, or oral JAK inhibitors;
- Cell depletion agents (e.g., rituximab) or other biological agents;
- Other investigational drugs (non CBP-201) or treatments.

Or the following prohibited drugs/treatments are used for a cumulative period of more than 7 days during Stage 2 (W16 to W52):

- Initiation of SIT, or dose up-regulation;
- TCS or TCI (topical drugs can be used for AD lesion areas only);
- Phototherapy (NBUVB, UVB, UVA1, PUVA), sunbed or any other LED therapies;
- Bleaching baths more than 2 times a week;
- Any drug for the treatment of AD (If topical drugs, only those used for AD lesion areas will be counted) that may interfere with the evaluation of efficacy results or affect the evaluation of AD severity.

Analysis method 2: The analysis will be performed using the actual observed values. If the actual observed value is missing, it will be imputed by MI.

During MI in Stage 2, M data sets will be generated by regression method (M is set as 1000 during Stage 2 analysis).

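### Stage 2 analysis method 1 counts short topical-type rescue only by total days and omits the 4-week recency test that the same SAP applies at W16

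*SAP*

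**What the plan says.** The point concerns the later SAP version, which contains the Stage 2 analysis; version 1.0 of 20 September 2022 defers it.

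**Stage 1 (SAP 7.4.2).** One list of treatments covers SIT changes, TCS or TCI, phototherapy, frequent bleach baths and other drugs for AD. I call these second-tier rescue. They are sorted by two tests, duration and recency.
- Intercurrent event 2 keeps the observed value when use "is no more than 7 days, and the end date is at least 4 weeks away from the W16 visit".
- Intercurrent event 3, use for poor response, is non-response when cumulative use "before the W16 visit is more than 7 days, or the end date is less than 4 weeks away from the W16 visit".
- Intercurrent event 6, use for other reasons, has the same two tests ("is more than 7 days, or the end date is less than 4 weeks away from the W16 visit") with a hypothetical strategy.

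**Stage 2 (SAP 7.4.5).** Method 1 says: "Categorical efficacy endpoints after the occurrence of events will be regarded as no response for subjects who have the following conditions". Continuous endpoints are imputed by WOCF. One of the conditions is rescue for poor response "which has a major impact on the assessment of the efficacy endpoints, including" two lists. Any use from the first list (systemic agents, biologics, topical PDE-4 or JAK inhibitors and so on) is enough. The second list is the second-tier one, and its only criterion is: "Or the following prohibited drugs/treatments are used for a cumulative period of more than 7 days during Stage 2 (W16 to W52"). No end date relative to any visit is mentioned. Under method 2, "The analysis will be performed using the actual observed values".

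**Endpoints and changes.** SAP 4.1.3 defines W52 response proportions, by-visit proportions to W60, and the share of W16 EASI-75 and IGA 0-1 responders who still qualify at W52. SAP 7.8 lists changes to endpoints and says nothing about the rescue rule.

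**The concern.** The plan uses the notion of major impact in both stages for the same kind of treatment, but defines it differently. At W16, a short course is harmless only if it was brief and also finished at least 4 weeks earlier. In Stage 2, brief is enough.

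The case is a realistic one. Protocol 8.2.2 makes TCS or TCI the first rescue step as far as possible and allows escalation only after at least 7 days of topical treatment without adequate response. A course that works within 7 days is what that step aims for, and it falls inside the uncounted zone.

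What is at stake is how the maintenance results can be read. Method 1 is the only Stage 2 analysis that sets aside rescue-influenced values. If it leaves in scores taken just after topical rescue, the W52 and by-visit rates mix drug effect with rescue effect. The maintained-response proportions would also judge their two ends, W16 and W52, by different rescue standards.

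**Working it through.** The plan states no figure on this point that could be reproduced, so the check compares the two rules.

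**Inputs.** Let d be cumulative days of second-tier rescue for poor response, and g the days from the end of use to the visit.
- W16 rule (SAP 7.4.2, events 2 and 3): non-response if d > 7 or g < 28; otherwise observed value.
- Stage 2 method 1 (SAP 7.4.5): non-response if d > 7; otherwise observed value.
- Length of Stage 2: D113 to D365 = 252 days = 36 weeks (Protocol 1.2).

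**Comparison.**

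| d | g | Rule at W16 | Method 1 at W52 |
|---|---|---|---|
| 1 | 0 | non-response | observed |
| 7 | 0 | non-response | observed |
| 7 | 27 | non-response | observed |
| 7 | 28 | observed | observed |
| 8 | 0 | non-response | non-response |
| 8 | 60 | non-response | non-response |

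The rules differ exactly where d is 1 to 7 and g is 0 to 27: 7 × 28 = 196 combinations, all classified differently. Outside that region they agree.

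**Does anything else catch these subjects?**
- Method 2 uses observed values whatever the rescue.
- Reassignment to Group E needs two consecutive assessments without EASI-50, so it misses a score held up by rescue.
- The protocol's intercurrent-event table (12.1) refers only to W16.
- The word introducing the two lists in 7.4.5 could be read as non-exhaustive, but no other criterion is given, so a programmer would apply only the 7-day count.

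**Size.** If k of N subjects in a denominator are observed responders at the visit with d ≤ 7 and g < 28, the reported proportion exceeds the one under the W16 logic by k/N. The documents give no k. As assumptions, k/N of 1%, 2%, 5% or 10% gives 1, 2, 5 or 10 points.

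For the weight of one subject, take the protocol's planned completers (144 and 72) and assume EASI-50 at W16 in 70% to 85% on CBP-201 and 30% to 45% on placebo:
- low: (144 × 0.70 + 72 × 0.30)/2 = (100.8 + 21.6)/2 = 61.2 per Stage 2 arm;
- high: (144 × 0.85 + 72 × 0.45)/2 = (122.4 + 32.4)/2 = 77.4 per Stage 2 arm.

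One subject then moves an all-subject proportion in Group C or D by 1/77.4 = 1.3 to 1/61.2 = 1.6 points. The maintained-response endpoints have smaller denominators, because they are restricted to W16 EASI-75 or IGA 0-1 responders. One subject weighs more there, but fewer subjects are eligible.

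**The case against.** The strongest case for the present rule is structural. Stage 1 has one target visit; Stage 2 has many, and a method 1 event makes later values non-response. Copying the Stage 1 recency test unchanged would turn one day of topical rescue into lasting failure. On duration, Stage 2 is even the stricter stage: the same 7-day allowance has to last 36 weeks rather than 16, and repeated short courses add up. First-list rescue counts with any use. Rescue is also visible elsewhere: recurrences, their days and the number of subjects affected from W16 to W52 are endpoints (SAP 4.1.3), and Stage 2 rescue treatments are summarised (SAP 7.3.6).

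All of this is correct. It shows that the recency test needs adapting, not that it can be dropped without comment. Separate recurrence tables do not correct the response proportions.

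The protocol's eligibility rule on "Topical drugs for treatment of AD or have the potential to affect the assessment of AD" gives limited support. It bars such drugs for 2 weeks before baseline, so it shows that recent topical use matters, but not that 4 weeks is the right window. The 4 weeks come from the SAP's own W16 rule.

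A reader might infer three stronger things that the documents do not support.
- *That anyone using topical rescue right up to W52 can count as a maintained responder.* This is possible only with 7 or fewer cumulative days over all of Stage 2; longer use is already non-response.
- *That the gap favours Q4W and hides a difference from Q2W.* No flare or rescue frequency by regimen is given. Protocol 4.4.4 describes both 300 mg regimens as more consistently better than 150 mg Q2W, which does not establish more flares on Q4W.
- *That efficacy conclusions are at risk.* No inferential statistics are planned for Stage 2.

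**Conclusion.** The point holds in a limited form. In method 1, second-tier rescue for poor response of 7 or fewer cumulative days, ending less than 4 weeks before a Stage 2 visit, leaves the observed value in the analysis. The same SAP calls that pattern non-response at W16 and gives no reason for the difference.

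This conclusion rests on the wording alone and is firm. The size is unknown: the 1 to 10 point range and the weight per subject depend on assumed frequencies. They also measure the gap between two rules rather than bias, since some of these subjects would have responded without rescue. Direction between Q2W and Q4W is unknown. The affected results are descriptive and belong to the other efficacy endpoints. The primary endpoint, key secondary endpoints and type I error are untouched. It is a cheap improvement to the Stage 2 reporting.

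**What to change.** In SAP 7.4.5 method 1:
1. Keep more than 7 cumulative days of second-tier rescue as the event with lasting effect.
2. Add a visit-specific rule: a visit value is non-response (continuous endpoints: WOCF) if any second-tier rescue for poor response ended less than 4 weeks before that visit or was still in use at it. Apply this only to visits inside that window; later visits return to the observed value unless another event applies.
3. State how the rule applies at W56 and W60, since by-visit endpoints run to W60 while the present count stops at W52.

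If the sponsor prefers the present rule as the main one, report the version above as a sensitivity analysis and justify the difference from W16 in SAP 7.8.

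The second rule adapts the Stage 1 test and is not a straight copy, so it needs its own definition and some per-visit programming. Rescue end dates are already needed for the W16 rule, and SAP 7.2.1 has conventions for incomplete ones. Reported Stage 2 response rates may be slightly lower. Data collection and patient care do not change.

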7.5. Safety Analysis

7.5.1. Drug exposure and compliance

Study drug exposure will be analyzed based on SS1, SS2 and SS3. Study drug exposure duration and exposure dose during treatment period of Stages 1 and 2 will be summarized by descriptive statistics.

The compliance with the study drug and emollients (background treatment) in Stages 1 and 2 will be summarized by descriptive statistics. The subjects with a compliance $< 70\%$, $\geq 70\%$ and $\leq 130\%$, and $> 130\%$ will be summarized, and the number and percentage of subjects will

be calculated. Subjects' compliance with the study drug and emollients (background treatment) will be tabulated.

7.5.2. AEs

AEs will be analyzed based on the SS1 and SS2. Subjects who have received at least one dose of the study drug will be analyzed based on SS3.

AEs will be coded using MedDRA.

The occurrence of overall AEs will be summarized to generate summary tabulations of TEAEs. TEAEs of special interest and drug-related AESIs will be summarized. The numbers of subjects with various AEs, numbers and incidences of events will be calculated. The number of subjects with various AEs, the number of events, the incidence and annual incidence of events will be calculated based on SS3.

AEs, drug-related AEs, SAEs, AESIs, AEs leading to death, AEs leading to treatment discontinuation, injection site AEs, CTCAE grade 3-5 AEs, AEs with an incidence of $> 5\%$, and AD recurrence-related AEs will be tabulated.

The incidences of the following TEAEs will be summarized by SOC and PT, the numbers of subjects with various AEs, and the numbers and incidences of events will be calculated. They will be ranked in descending order of total number of subjects by SOC and PT. In addition, annual incidences of TEAEs, treatment-emergent SAEs, treatment-emergent AESIs, drug-related AEs, drug-related SAEs will be calculated by SOC and PT based on SS3.

- 1) TEAEs;
- 2) Drug-related AEs;
- 3) SAEs;
- 4) Drug-related SAEs;
- 5) AEs leading to death;
- 6) AEs leading to treatment discontinuation;
- 7) AEs leading to treatment interruption;
- 8) AESIs;
- 9) Drug-related AESIs;
- 10) Injection site AEs;
- 11) CTCAE grade 3-5 AEs;
- 12) AEs with an incidence of $> 5\%$;

In addition, the incidences of TEAEs, AESIs, and injection site AEs will be summarized by CTCAE Grade, correlation with study drug, SOC and PT, and the number and percentage of subjects will be calculated.

A subject with an AE of the same SOC and PT more than once will have that event counted only once within each SOC and PT.

7.5.3. Laboratory test results

Analysis will be performed based on SS1, SS2 and SS3. Analysis will not be performed using SS3 by visit.

The hematology, blood biochemistry and urinalysis parameters at baseline and each visit and their changes from baseline at each visit will be summarized by descriptive statistics.

The number and percentage of subjects whose hematology, blood biochemistry and urinalysis parameters at baseline and each visit are below, within and above the normal range will be summarized.

Pre-treatment and post-treatment laboratory test results are classified into abnormal with clinical significance, abnormal without clinical significance, normal, and not tested in an order of abnormal with clinical significance > abnormal without clinical significance > normal > not tested. Then shift tables are generated. The shift tables are generated based on CTCAE 5.0.

All laboratory test results and abnormal laboratory test results for hematology, blood biochemistry, urinalysis and urine pregnancy will be tabulated.

Qualitative laboratory test results will be summarized by visit. The number and percentage of subjects for each category will be calculated and tabulated.

7.5.4. ECG

Analysis will be performed based on SS1, SS2 and SS3. Analysis will not be performed using SS3 by visit.

Ventricular rhythm, PR, QRS, QT and QTcF results at each post-baseline visit and their changes from baseline at each visit will be summarized by descriptive statistics. The analysis of variance will be used to detect possible difference between groups.

Special attention will be paid to QTcF interval prolongation:

- QTcF interval > 450 ms
- QTcF interval > 480 ms
- QTcF interval > 500 ms
- Increase in QTcF interval from baseline > 30 ms
- Increase in QTcF interval from baseline > 60 ms

Pre-treatment and post-treatment ECG results are classified into abnormal with clinical significance, abnormal without clinical significance, normal, and not tested in an order of abnormal with clinical significance > abnormal without clinical significance > normal > not tested. Then shift tables are generated.

ECG results of QTcF interval prolongation will be tabulated. All ECG results and clinically significant abnormal ECG results will be tabulated.

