After all subjects (including approximately 81 additional subjects enrolled) entering Stage 2 have completed the treatment, evaluations and follow-up of Stage 2, a Stage 2 analysis will be performed. Statistical inference will not be performed during the Stage 2 analysis.

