Descriptive statistics will be used to summarize the baseline value of laboratory test results and the changes from baseline to each visit.

- According to laboratory-wide specifications, clinical laboratory parameters will be classified into low, normal, or high, and the number and percentage of subjects in each category will be summarized.
- Shift tables based on normal/abnormal baseline values and other tabular and graphical methods may be used to display the results of laboratory tests of interest.
- Lists with flags that indicate values outside the laboratory's range will be provided.

Vital signs

Descriptive statistics will be used to summarize the baseline values of vital signs (body temperature, pulse, blood pressure, and respiratory rate) and the changes from baseline to each visit.

Other safety data, including eye examination results, PE, 12-lead ECG results, and ADA test results will be classified and summarized, and the frequency and percentage of each category will be listed.

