3.1. Overall Design

This study is a randomized, double-blind, multi-center, controlled study designed to assess the efficacy, safety, and PK characteristics of CBP-201 in eligible subjects with moderate to severe AD. 255 subjects will be randomized in a 2:1 ratio to receive either CBP-201 300 mg Q2W or placebo.

The study includes a screening period, a treatment period and a follow-up period. The treatment period is divided into two stages:

Stage 1 study: It is a placebo-controlled study, in which subjects who meet the inclusion criteria and do not meet the exclusion criteria will be stratified according to the severity of their baseline disease (moderate [IGA=3] and severe [IGA=4]) and randomized into one of the following 2 groups to receive investigational product or placebo treatment by the ratio of 2:1:

- Group A (CBP-201): the subjects will receive a subcutaneous injection of CBP-201 600 mg (4 ml in total, 2 injections of 2 ml each in different sites) on Day 1, begin to receive a subcutaneous injection of CBP-201 300 mg (2 ml) from Week 2 (W2), and receive treatment at the same dose every 2 weeks thereafter until W14;
- Group B (placebo): the subjects will receive a subcutaneous injection of placebo 4 ml (2

injections of 2 ml each in different sites) on Day 1, begin to receive a subcutaneous injection of placebo 2 ml from W2, and receive placebo 2 ml every 2 weeks thereafter until W14.

Table 1: Dosing Regimen by Group in Stage 1

Group	W0	W2	W4	W6	W8	W10	W12	W14
Group A	4XC	2XC						
Group B	4XP	2XP						

Note: C=CBP-201; P=placebo; #X=number of ampoules.

Before the administration of study drug at W16 visit, all subjects will be assessed for efficacy, and the treatment assignment for Stage 2 maintenance treatment is based on whether a subject achieves a 50% or greater reduction in Eczema Area and Severity Index (EASI) score (ie EASI-50).

Stage 2 study: The grouping for Stage 2 maintenance treatment is as follows:

- Subjects who have achieved EASI-50 in the W16 pre-administration efficacy assessment will be randomized in a 1:1 ratio into one of the following two groups to receive study treatment starting from W16:
 - Group C: The subjects will receive a subcutaneous injection of CBP-201 300 mg every 2 weeks until W50;

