7.5.5. Other safety evaluation

The following analyses will be performed based on SS1, SS2 and SS3. Analysis will not be performed using SS3 by visit.

Physical examination

Physical examination results at each visit in Stages 1 and 2 will be classified into abnormal with clinical significance, abnormal without clinical significance, normal and not tested. The frequency and percentage of each category will be summarized.

All physical examination results and abnormal physical examination results with clinical significance will be tabulated.

Vital signs

The vital signs at baseline and their changes from baseline at each visit of Stages 1 and 2 will be summarized by descriptive statistics. The analysis of variance will be used to detect possible difference between groups.

Vital sign results at each visit of Stages 1 and 2 will be classified into abnormal with clinical significance, abnormal without clinical significance, normal and not tested. The frequency and percentage of each category will be summarized.

All vital sign results and abnormal vital sign results with clinical significance will be tabulated.

Eye examination

Eye examination results at each visit of Stages 1 and 2 will be classified into abnormal with clinical significance, abnormal without clinical significance, normal and not tested. The frequency and percentage of each category will be summarized.

All eye examination results and abnormal eye examination results with clinical significance will be tabulated.

ADA test

See PK/PD statistical analysis plan for details.

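### The ECG and vital-sign ANOVA is not limited to Stage 1, so as written it tests Groups C, D and E in Stage 2, where the protocol rules out inference

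*SAP*

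**What the plan says.** SAP 7.5.4 (ECG) sets its scope with "Analysis will be performed based on SS1, SS2 and SS3" and one limit, "Analysis will not be performed using SS3 by visit". It asks for a by-visit summary of post-baseline values and changes from baseline, and then adds "The analysis of variance will be used to detect possible difference between groups". SAP 7.5.5 has the same scope and limit. For vital signs it says "The vital signs at baseline and their changes from baseline at each visit of Stages 1 and 2 will be summarized by descriptive statistics", followed by the same ANOVA sentence. Neither section gives the response variable, the model terms or an exploratory label.

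Protocol 12.5, the general analysis plan, says "Statistical inference will not be performed during the Stage 2 analysis". SAP 7.4.5 has a parallel sentence for Stage 2 efficacy: "Inferential statistics will not be performed during the Stage 2 analysis".

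Protocol 12.8 plans no between-group test for these data. For vital signs it says "Descriptive statistics will be used to summarize the baseline values of vital signs" and the changes from baseline. ECG results are to be shown as category counts and percentages. SAP 7.8, which lists changes from the protocol, covers efficacy endpoints only.

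On the Stage 2 groups, SAP 3.1 says that W16 EASI-50 responders "will be randomized in a 1:1 ratio into one of the following two groups to receive study treatment starting from W16", namely C (300 mg Q2W) and D (300 mg Q4W). Non-responders go to Group E (300 mg Q2W) without randomisation. SAP Table 4 lists C, D and E as the SS2 treatment groups.

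**The concern.** Read literally, the SAP calls for p-values on ECG and vital-sign changes across C, D and E. The protocol says Stage 2 will have none, and the departure is not declared.

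The p-values would also be hard to use. Group E is selected on poor response, so any test that includes it mixes regimen with response status. SAP 7.1 labels P < 0.05 as statistically significant unless otherwise specified, and nothing in 7.5.4 or 7.5.5 specifies otherwise. A chance or selection-driven difference in QTcF or blood pressure could therefore be reported as a significant safety finding, or a null result taken as reassurance, without a valid comparison behind it.

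In SS1 the issue is smaller. The model is not stated. If it omits the baseline value, a comparison meant to detect safety signals is less precise than the collected data allow.

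**Working it through.** The plan states no figure for these comparisons, so there is none to reproduce.

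**1. Does the ANOVA reach SS2?** SAP 7.5.4 and 7.5.5 list SS2 at the top, and the only exclusion concerns SS3 by visit. In 7.5.5 the sentence just before the ANOVA covers both stages. SAP 7.5.3 (laboratory tests) has the same sets and layout but no ANOVA. SAP 1.0 carried the same ANOVA sentence with SS1 as the only set. The likely explanation is that the sets were widened and the sentence stayed; that is an inference.

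**2. What would an SS2 test compare?**

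| Contrast | Regimen from W16 | How groups were formed | Treatment reading |
|---|---|---|---|
| C vs D | Q2W vs Q4W | Randomised 1:1 among W16 responders | Possible |
| C vs E | Q2W vs Q2W | Responder vs non-responder | None: same regimen |
| D vs E | Q4W vs Q2W | Responder vs non-responder | Confounded with response |

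An overall three-group F test mixes all three rows. In addition, C and D subjects who miss EASI-50 at two consecutive assessments move to E, and SS2 groups subjects by treatment received.

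**3. How many p-values?** The SAP does not say whether the ANOVA is run at every visit. If it is, the inputs for vital signs are 5 parameters (SAP 4.2.5), 18 visits from W18 to W52 every two weeks ((52 − 18)/2 + 1 = 18), and 2 safety baselines (SAP 7.1):

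5 × 18 × 2 = 180 tests; 180 × 0.05 = 9 expected below 0.05 by chance, even if all groups were alike.

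**4. What does the baseline covariate gain in SS1?** Assume equal variances at baseline and visit, with correlation r. The documents give no r and no SD for any ECG or vital-sign parameter, so a range is shown. In units of the single-visit variance:

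- ANOVA on change: residual variance 2(1 − r)
- ANOVA on the post-baseline value: 1
- ANCOVA: 1 − r²

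Standard-error ratio, ANCOVA to change-score ANOVA: √[(1 − r²)/(2(1 − r))] = √[(1 + r)/2]. ANCOVA to raw-value ANOVA: √(1 − r²).

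| r | vs change score | SE reduction | vs raw value | SE reduction |
|---|---|---|---|---|
| 0.3 | √0.65 = 0.806 | 19% | √0.91 = 0.954 | 5% |
| 0.5 | √0.75 = 0.866 | 13% | √0.75 = 0.866 | 13% |
| 0.7 | √0.85 = 0.922 | 8% | √0.51 = 0.714 | 29% |
| 0.8 | √0.90 = 0.949 | 5% | √0.36 = 0.600 | 40% |

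The gain depends on which response is meant, which is one reason to name it. In randomised SS1 all three analyses estimate the same treatment difference without bias.

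**The case against.** The strongest reply is that the no-inference rule concerns efficacy. SAP 7.4.5 states it inside the efficacy section, and the protocol synopsis places it straight after the efficacy testing sequence. That is a fair reading of those two places. It does not cover Protocol 12.5, which is the general analysis plan and carries no such limit, nor Protocol 12.8, which plans descriptive safety summaries.

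A second reply is that the SS1 ANOVA was pre-specified in SAP 1.0, signed in September 2022. The current SAP cites a blinded review meeting in October 2023 for the final analysis, and the protocol planned Stage 1 unblinding once the 255 subjects finished Stage 1. Unblinding had therefore probably happened, although no date is given. Replacing a pre-specified model at that point for a modest precision gain would be hard to defend. This stands, and it shapes the fix.

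Four stronger readings are tempting, and the documents do not support them:

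- **All SS2 comparisons are non-randomised.** C versus D is randomised; only contrasts with E are not.
- **An ANOVA on SS3 is planned.** The ANOVA follows a by-visit summary, and by-visit analysis on SS3 is excluded. Whether the test applies there is unclear.
- **The SS1 ANOVA is biased, or ignores baseline.** No model terms are given, and a change score already contains the baseline. Omitting the covariate costs precision only.
- **The SS2 test has a known inflated error rate.** A simulation of change-score ANOVA gave 8% to 28% false positives, but only by assuming group sizes of 75, 75 and 60 and a baseline shift of 0.25 to 0.5 SD in Group E. With no shift it was about 5%. Nothing in the documents links EASI non-response to ECG or vital signs, so this figure is not relied on.

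**Conclusion.** The concern holds as a conflict of wording with a real but minor consequence. As written, the ECG and vital-sign ANOVA extends to SS2, against Protocol 12.5 and beyond the descriptive plan in Protocol 12.8, and SAP 7.8 does not declare it. Any contrast with Group E lacks a treatment interpretation at any sample size; this follows from the design and needs no numerical assumption. The count of 180 vital-sign tests holds only if the ANOVA is run at every visit and for both baselines.

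The SS1 part is an optional improvement: a standard error about 19% to 5% smaller for r from 0.3 to 0.8, if the response is change from baseline. These are safety comparisons outside the efficacy testing sequence, so the primary conclusion does not depend on them.

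**What to change.** In SAP 7.5.4 and in the vital-signs part of 7.5.5:

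1. State that the between-group comparison applies to SS1 only, is exploratory, and carries no multiplicity control. State that SS2 and SS3 are summarised descriptively.
2. Name the response (for example, change from baseline at each scheduled visit) and the model. Add the parameter's baseline value as a covariate (ANCOVA), and report the treatment difference with its 95% confidence interval.
3. If Stage 1 was unblinded before this change, keep the ANOVA from SAP 1.0 and present the ANCOVA beside it, labelled as added later.
4. List the SS1 test in SAP 7.8 as a departure from the protocol's descriptive safety plan.

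The cost is a few sentences of SAP text and one model statement per parameter, with no new data. The downside of item 2 is a departure from the pre-specified SS1 ANOVA, which item 3 contains. Items 1 and 4 can be adopted without item 2.
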